Official Title: Management of Spontaneous Ruptured Hepatocellular Carcinoma

- Partial Hepatectomy and Prognosis: A Retrospective Study

NCT number: Not available

Date of the document: 05/03/2018

Statistical analysis plan

All of the analyses were carried out using SPSS 24.0 (IBM), and a two-sided $P < 0.05$ was considered statistically significant.

1. A comparison of the clinicopathologic characteristics of all the patients between the partial hepatectomy group and the non-surgical treatment group before propensity score matching (PSM): there are (or no) significances for patients' characteristics before PSM.

The variables are: age, sex, HBs-Ag (+), HCV-Ab, tumor size, tumor number, macroscopic vascular invasion (MVI), cirrhosis, portal hypertension, Child-Pugh grade, hemorrhagic shock, hemoglobin, red blood cell (RBC), transfusion during hospitalization, a-fetoprotein (AFP), aspartate aminotransferase (AST), albumin, total bilirubin, Barcelona Clinic Liver Cancer (BCLC) stage, sorafenib, 30-day mortality.

Statistical analysis method: Pearson's χ^2 test, χ^2 test with Yates' correction, Fisher's exact test, Wilcoxon's rank-sum test and Student's t test.

2. Univariate and multivariate analysis of the predictive factors associated with overall survival (OS) before PSM: surgery or non-surgical treatment is (or not) an independent risk factor of overall survival.

The variables included are: age, sex, tumor size, tumor number, MVI, cirrhosis, portal hypertension, treatment, hemorrhagic shock, distant metastasis, AST, AFP, platelet, hemoglobin, sorafenib, Child-Pugh grade.

Statistical analysis method: univariate analysis was performed using the Kaplan-Meier method compared by the log-rank test; multivariate analysis was performed using the COX regression model.

3. A comparison of the clinicopathologic characteristics of all of the patients between the partial hepatectomy group and the non-surgical treatment group after PSM: there is no significance for patients' characteristics after PSM.

The variables included in PSM are: age, sex, tumor size, tumor number, MVI, cirrhosis, portal hypertension, hemorrhagic shock, hemoglobin, red blood cell (RBC), transfusion during hospitalization, a-fetoprotein (AFP), aspartate aminotransferase (AST), albumin, total bilirubin.

Statistical analysis method: PSM, a caliper of 0.5, 0.3, 0.2, 0.1, 0.05, 0.02, 0.01 would be used.

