4. Univariate and multivariate analysis of the predictive factors associated with OS after PSM: surgery or non-surgical treatment is (or not) an independent risk factor of overall survival.

The variables included are: age, sex, tumor size, tumor number, MVI, cirrhosis, portal hypertension, treatment, hemorrhagic shock, distant metastasis, AST, AFP, platelet, hemoglobin, Sorafenib, Child-Pugh grade.

Statistical analysis method: univariate analysis was performed using the Kaplan-Meier method compared by the log-rank test; multivariate analysis was performed using the

COX regression model.

5. Comparison of OS and recurrence-free survival (RFS) between the emergency partial hepatectomy group and the staged partial hepatectomy group.

Statistical analysis method: univariate analysis was performed using the Kaplan-Meier method compared by the log-rank test.

6. Comparison of OS and RFS between the staged early partial hepatectomy group and the staged late partial hepatectomy group.

Statistical analysis method: univariate analysis was performed using the Kaplan-Meier method compared by the log-rank test.

7. Difference in 30-day mortality of peritoneal dissemination between the groups at different times.

Statistical analysis method: Pearson's χ^2 test, χ^2 test with Yates' correction and Fisher's exact test.

8. Univariate and multivariate logistic regression analysis of postoperative peritoneal dissemination.

The variables included are: age, sex, tumor size, tumor number, MVI, cirrhosis, estimated intraperitoneal bleeding, Child-Pugh grade, tumor differentiation, resection margin, type of hepatectomy, timing of hepatectomy.

Statistical analysis method: univariate and multivariate logistic regression analysis.

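### SAP items 5 and 6 compare OS only among patients who reached their hepatectomy, so if early mortality is high, staged and late resection look better even when timing has no effect

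*SAP*

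**What the plan says.** The title calls the work "Partial Hepatectomy and Prognosis: A Retrospective Study", so groups are formed from care received and not from assignment. Items 1 and 3 contrast two groups, the first of them "of all the patients between the partial hepatectomy group and the non-surgical treatment group".

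Within the operated patients, item 5 is a "Comparison of OS and recurrence-free survival (RFS) between the emergency partial hepatectomy group and the staged partial hepatectomy group", and item 6 a "Comparison of OS and RFS between the staged early partial hepatectomy group and the staged late partial hepatectomy group". For both, the only method is this: "univariate analysis was performed using the Kaplan-Meier method compared by the log-rank test". Neither item mentions a time origin, a landmark, delayed entry, a time-dependent exposure, a group defined by intended strategy, or any covariate adjustment. The significance level is two-sided 0.05 throughout.

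**The concern.** A patient belongs to the staged group, and still more to the staged late group, only by living from rupture to that operation and remaining resectable. One who was managed towards a staged resection and died first had no hepatectomy, and so would be counted among the non-surgical patients in items 1 to 4 and nowhere in items 5 and 6. The emergency group, operated on at once, keeps all its early deaths. Membership thus depends on the outcome being compared, and more strongly the longer the wait.

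Neither usual time origin removes this under the stated method. Counted from rupture, the wait is survival time that a staged patient cannot fail to have. Counted from operation, that guaranteed time is gone, but staged patients have already passed part or all of the high-hazard period that emergency patients carry in full. Adding covariates would not bring back the missing deaths. The practical stake is that a log-rank difference in items 5 or 6 could be reported as a survival benefit of delay when timing has none.

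**Working it through.** The SAP states no sample size, event rate or effect size, so there is no figure of the plan to reproduce. Every rate below is an assumption chosen to show the mechanism. All calculations in steps 1 to 3 assume that timing has **no** effect on survival. They model death while waiting, not loss of resectability.

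**Step 1. Closed form.** Let d be the proportion dead by day 30 after rupture, and let 60% of day-30 survivors be alive at day 365. Then

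S(t) = (1 − d)^(t/30) for t ≤ 30, and S(t) = (1 − d) × 0.6^((t − 30)/335) for t > 30.

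Emergency patients follow S(t). Staged patients operated on at day w are seen only if alive at w, so they follow S(t)/S(w) from rupture and S(t + w)/S(w) from operation. With d = 0.20 and w = 30:

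- lost before operation: 1 − 0.80 = 20%
- one-year survival, emergency: 0.80 × 0.60 = 48%
- one-year survival, staged, from rupture: 0.48/0.80 = 60%
- one-year survival, staged, from operation: 0.6^(365/335) = 57%

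The underlying survival is identical, yet staged appears 12 or 9 percentage points better. With d = 0.10 the emergency figure is 54%, and with d = 0.30 it is 42%. The staged figures do not change. For a short wait (w = 10, d = 0.20) the gap shrinks: 7% are lost, and one-year survival is 52% from rupture or 51% from operation, against 48%.

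**Step 2. Simulated hazard ratio with a spread of operation dates.** Assumed: 80 emergency patients, 120 intended for staging, staged operation uniformly on days 3 to 60, exponential survival after day 30 with a 12-month median, 5-year follow-up.

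| Dead by day 30 | OS HR staged vs emergency, from rupture | from operation |
|---|---|---|
| 5% | 0.93 | 0.99 |
| 20% | 0.83 | 0.89 |
| 30% | 0.76 | 0.81 |

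With the median set at 12 or 24 months, the log-rank test rejects the true null hypothesis in 22–27% of runs from rupture and 12–19% from operation at 20% early deaths, and in 40–46% and 27–37% at 30%. The nominal rate is 5%. For item 6, with an assumed early/late cut at day 14 and 20% early deaths, late against early gives 0.83 from rupture and 0.86–0.89 from operation.

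**Step 3. A different set of assumptions.** With 100 patients per group, every staged operation on day 30, the survival curve of step 1 and 3-year follow-up, the HR is 0.88, 0.77 and 0.67 from rupture at 10%, 20% and 30% early deaths, and 0.93, 0.81 and 0.71 from operation. With every operation on day 10 it is 0.96 to 0.87 from rupture and 0.98 to 0.91 from operation. The direction is the same; the size depends on early mortality and on the length of the wait.

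**Step 4. What delayed entry does and does not do.** In the step 2 set-up, timing everyone from rupture and admitting each resected patient to the risk set on the day of operation returns an HR of about 1.00 at both 20% and 30% early deaths. The spurious advantage disappears. But if waiting is made harmful (20% early deaths, hazard while waiting doubled or tripled), comparing the whole strategies from rupture gives an HR of 1.19 or 1.38, while the delayed-entry HR stays at about 1.01. Delayed entry corrects the comparison of operated patients. It does not put the waiting deaths into the contrast.

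**The case against.** The SAP defines none of emergency, staged, early or late, and gives no time origin; a protocol may do so. That is fair: the composition of the groups is inferred. But the inference rests on three things that agree: groups named after a hepatectomy, a retrospective design, and RFS, which presupposes a resection. Under that reading, the choice of time origin does not rescue the stated method when the early hazard is raised.

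Items 5 and 6 say only that groups are compared. Unlike items 2 and 4, they do not speak of an independent risk factor. A reader might infer that the plan sets out to show which timing strategy is better, but the document does not say so, and outcome by timing among resected patients is a legitimate conditional description. This limits the point to how OS is analysed and interpreted. It does not remove it, because even the conditional comparison is distorted when patients are not aligned on time since rupture.

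A reader might also extend the point to item 7 and infer a spurious difference in 30-day mortality. Its endpoint reads "Difference in 30-day mortality of peritoneal dissemination between the groups at different times", which could mean mortality, dissemination or both. That wording cannot carry such a claim, so item 7 is left out.

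Finally, with 5% early deaths and time counted from operation, the bias is negligible. This stands, and the conclusion is conditional for that reason.

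**Conclusion.** The point holds for OS in items 5 and 6, on the reading that only operated patients are in the groups. If the hazard is raised early after rupture, the planned log-rank comparison favours staged over emergency and late over early without any timing effect. Under the assumptions of step 2, the distortion runs from almost nothing (HR 0.99 from operation at 5% early deaths) to substantial (0.76 from rupture at 30%).

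It would go too far to say that the study will find delay beneficial, or that the published difference would be biased by any particular amount. The SAP supplies no mortality rates, waiting times or cut-point. Items 5 and 6 are also unadjusted for severity, whose effect may run either way, so neither the direction nor the size of the net bias can be derived. It would also be wrong to infer that delayed entry settles which timing is better; step 4 shows that it does not.

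**What to change.** - **OS, items 5 and 6.** Count time from rupture (or admission) for every patient, and let each resected patient enter the risk set on the day of operation, using delayed-entry Kaplan-Meier and Cox. Alternatively, fit a Cox model in the whole cohort with a time-dependent operation state (not yet operated, emergency, staged early, staged late).
- **Interpretation.** State that this hazard ratio compares patients who reached resection at equal time since rupture, does not include deaths while waiting, and therefore does not show which timing strategy is better.
- **Strategy comparison.** Where the records identify candidates for staged resection, add a comparison from rupture that keeps those who died waiting in the staged strategy. No variable listed in the SAP identifies them at present, so this may not be feasible.
- **RFS.** Label it as conditional on reaching resection and draw no conclusion about the choice of timing from it.
- **Item 7.** If it is meant as 30-day postoperative mortality by timing, give it the same label.

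The cost is SAP wording, one further Cox model and two dates per patient (rupture or admission, and operation); the non-surgical patients are already in the cohort. The price is wider intervals and little information about the first days after rupture, before staged operations begin.

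### Item 8 lists 12 variables for ordinary logistic regression of peritoneal dissemination with nothing tying model size to events; if events are few, adjusted odds ratios for real effects would be overstated and unstable

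*SAP*

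**What the plan says.** Item 8 of the SAP is headed "Univariate and multivariate logistic regression analysis of postoperative peritoneal dissemination". Its variable list opens with "age, sex, tumor size, tumor number, MVI, cirrhosis, estimated intraperitoneal bleeding" and ends with "estimated intraperitoneal bleeding, Child-Pugh grade, tumor differentiation, resection margin, type of hepatectomy, timing of hepatectomy"; bleeding appears in both quotes, and the list has 12 variables in all. The method line reads "Statistical analysis method: univariate and multivariate logistic regression analysis".

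The item gives no coding of the variables, no rule for moving from the univariate to the multivariate step, no limit on parameters relative to events, and no method for sparse data. The opening paragraph says that all analyses use SPSS 24.0 and that "a two-sided $P < 0.05$ was considered statistically significant".

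Items 5 and 6 bear on how timing might be coded. Item 5 contrasts emergency with staged resection. Item 6 is a "Comparison of OS and RFS between the staged early partial hepatectomy group and the staged late partial hepatectomy group". The SAP states neither the number of resections nor the number of dissemination events.

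**The concern.** The outcome is postoperative, and the margin, type and timing of resection exist only for operated patients. The model therefore uses one arm of a retrospective cohort, and within that arm only patients who disseminate are events. Twelve variables cost at least 12 parameters. When events per parameter are low, ordinary maximum likelihood estimates of non-null log odds ratios are biased away from zero and have a large variance. Some data sets also separate, so that no finite estimate exists.

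The matter is more than cosmetic because item 8 is the SAP's only adjusted analysis that includes timing of surgery. Items 5 and 6 use unadjusted log-rank tests, item 7 uses contingency-table tests, and the Cox models in items 2 and 4 include treatment but not timing. If the adjusted timing odds ratio were overstated, no other adjusted result in the plan would show it.

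**Working it through.** The plan gives no figure to reproduce, so the check is a count followed by simulation.

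**Inputs.** From item 8: 12 variables and ordinary logistic regression. From the opening paragraph: two-sided 5% significance. Assumed: numbers of resections and events, variable coding and true effect sizes.

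**Parameters.** With every variable binary or linear there are 12. If timing has three levels (suggested by items 5 and 6) and differentiation has three levels (an assumption), there are 12 + 1 + 1 = 14.

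**Benchmark.** Ten events per parameter, a rule of thumb only, would need 12 × 10 = 120 to 14 × 10 = 140 events. At an assumed 15–25% event rate that is 120/0.25 = 480 to 140/0.15 = 933 resections.

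**Simulation with a true odds ratio of 2.5.** The 14-parameter runs used 100, 150 or 250 resections and 1,500 replicates each. The 12-parameter runs used binary covariates. The ratio is the estimate divided by 2.5.

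| Events | Events per parameter (14 / 12) | Ordinary OR, 14 parameters (ratio) | Ordinary OR, 12 parameters (ratio) |
|---|---|---|---|
| 15 | 1.1 / 1.25 | 3.7 (1.48) | 3.2 (1.28) |
| 22 | 1.6 / 1.8 | 3.0 (1.20) | 2.9 (1.16) |
| 37 | 2.6 / 3.1 | 2.9 (1.16) | 2.7 (1.08) |
| 62 | 4.4 / 5.2 | 2.7 (1.08) | 2.7 (1.08) |
| 100–150 | 7.1–10.7 / 8.3–12.5 | not run | 2.5–2.6 (1.00–1.04) |

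Firth's penalised fit gave 2.5 with 14 parameters and 2.4–2.5 with 12. In the 14-parameter runs:

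- With 15 events in 100 resections, the root mean squared error of the log odds ratio was 1.27 for the ordinary fit and 0.78 for Firth, and 3% of ordinary fits failed.
- With 22 events in 150 resections, the errors were 0.76 and 0.59.
- Interval coverage was about 93% for the ordinary fit and 95–97% for Firth.

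In the 12-parameter runs the two errors were equal by 150 events.

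**Simulation with a true odds ratio of 2.0.** There were 1,500 data sets per setting, with four continuous covariates and the rest binary. Values are geometric mean odds ratios; ordinary fits that separated or did not converge are excluded.

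| Patients / events | Ordinary, 12 | Ordinary, 14 | Failed fits (12 / 14) | Firth (12 / 14) |
|---|---|---|---|---|
| 80 / 10 | 2.70 | 2.83 | 28% / 30% | 2.00 / 2.01 |
| 100 / 20 | 2.37 | 2.59 | 1.5% / 1.3% | 1.98 / 2.06 |
| 130 / 30 | 2.26 | 2.32 | 0.2% / 0.3% | 2.02 / 2.03 |
| 200 / 40 | 2.16 | 2.17 | 0 / 0 | 2.01 / 2.00 |
| 300 / 70 | 2.10 | 2.08 | 0 / 0 | 2.01 / 1.99 |
| 500 / 140 | 2.04 | 2.06 | 0 / 0 | 1.99 / 2.01 |
| 800 / 200 | 2.03 | 2.05 | 0 / 0 | 2.00 / 2.02 |

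**Null factors.** With a true odds ratio of 1, the 12-parameter runs gave ordinary estimates of 0.98–1.01 and a rejection rate of about 5%.

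**The case against.** The strongest reply is that the SAP does not show events to be few. It gives neither resections nor events, and cohort size may properly stand in the protocol, which is not shown. That an outcome occurs in only some patients is true of any binary outcome. A reader might infer that the item 8 odds ratios are in fact inflated; the document does not support that, and the simulated inflation is only 2–5% at 70 or more events. This part of the reply stands.

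Three narrower points also stand. Fourteen parameters is an assumption, and only the 12 variables are written. Entering all 12 in one model is the natural reading of a single list, but it is not stated outright. A univariate screen might shrink the model, although none is specified and screening would bring its own selection bias. Finally, a reader might infer that every listed factor would be exaggerated or falsely declared significant. Null factors are not shifted and were rejected at about the nominal rate.

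It is also fair to say that imprecision outweighs bias. At 22 events the bias is ln(3.0/2.5) = 0.18, and 0.18²/0.76² is about 6% of the mean squared error. At 15 events ln(3.7/2.5) = 0.39, and 0.39²/1.27² is about 10%. That limits the severity. It does not defend the ordinary fit, because Firth reduces total error as well as bias in the sparse settings.

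**Conclusion.** The point holds as a conditional weakness of the stated method. Item 8 names a 12-variable ordinary logistic model in resected patients, with no link between model size and events and no provision for sparse data. If all 12 variables enter and events number about 15 to 60, odds ratios for real effects would be overstated by roughly 8% (62 events) to 28–48% (15 events), with wide error and occasional separation. Near 100 events and above, the bias is a few percent or less. These sizes rest on assumed event counts, coding and true effects, and on simulated covariates; none comes from the SAP. The change is still worth making without knowing the count, because the penalised fit removes the bias where it exists and alters little where events are many.

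**What to change.** In item 8, specify that the multivariable model is fitted by Firth's penalised likelihood with profile-likelihood confidence intervals. Keep the listed variables: moving the operative and pathological factors to univariate-only reporting would give up adjustment for them, which is a debatable trade. Report the number of dissemination events, and the number of parameters fitted, beside the model. Amend the opening software statement if the routine lies outside SPSS 24.0.

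The cost is SAP wording, possibly a second package, and a slightly conservative test: at 22 events, rejection for a true odds ratio of 2.5 was about 38–44% instead of 44–48%. The change does not cure imprecision, so with few events the intervals will remain wide.
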